3. LIST OF ABBREVIATIONS AND DEFINITION OF TERMS

Abbreviation	Definition of Term
AE	Adverse event
API	Average pain intensity
ATC	Around-the-clock
BMI	Body mass index
BPN	Buprenorphine
C-SSRS	Columbia-Suicide Severity Rating Scale
CGI-I	Clinical Global Impression of Improvement scale
CFR	Code of Federal Regulations
CI	Confidence interval
CLBP	Chronic low back pain
CNS	Central nervous system
COWS	Clinical Opiate Withdrawal Scale
CRF	Case Report Form (may include electronic data capture systems or paper forms)
CS	Clinically significant
CSA	Clinical Study Agreement
C _{ss,av}	Average concentration during a dosage interval at steady state
C _{ss,trough}	Trough concentration during a dosage interval at steady state
CYP3A4	Cytochrome P450 3A4
ECG	Electrocardiogram
EDC	Electronic data capture
EEW	Enriched-enrollment withdrawal
EQ-5D-5L	EuroQoL Group 5-dimension 5-level self-report questionnaire
FC	FluidCrystal
FDA	Food and Drug Administration
G	Gauge
GCP	Good Clinical Practice
HIV	Human Immunodeficiency Virus
ICF	Informed consent form
ICH	International Conference on Harmonization
IFU	Instructions for user
IM	Intramuscular
IMMPACT	Initiative on Methods, Measurement, and Pain Assessment in Clinical Trials
IR	Immediate-release
IRB	Institutional Review Board
ITT	Intent-to-Treat

Abbreviation	Definition of Term
IV	Intravenous
MED	Morphine equivalent dose
MMRM	Mixed Model Repeated Measures
Ms	milliseconds
NCS	Not clinically significant
norBPN	Norbuprenorphine
NRS-11	11-Point numerical rating scale
PGI-I	Patient Global Impression of Improvement scale
PK	Pharmacokinetic
Prn	As needed
q1w	Once weekly
q4-6h	Every 4 to 6 hours
q4w	Once monthly
QID	Four times daily
QTcF	QT interval corrected using Fridericia's formula
SAE	Serious adverse event
SAP	Statistical analysis plan
SC	Subcutaneous
SL	Sublingual
SOC	System Organ Class
SOWS	Subjective Opiate Withdrawal Scale
TID	Three time daily
ULN	Upper limit of normal
US	United States
WAAPI	Weekly Average of (Daily) Average Pain Intensity
WAWPI	Weekly Average of (Daily) Worst Pain Intensity
WHO	World Health Organization
WPAI	Work Productivity and Activity Impairment
WPI	Worst pain intensity

4. INTRODUCTION

4.1. Background

Opioids are recommended for the management of moderate to severe pain that cannot be well-controlled using non-opioid analgesics or other interventions ([American Academy of Pain Medicine, 2013](#); [Chou et al, 2009](#)). Buprenorphine (BPN) is an opioid with mixed agonist-antagonist properties that is currently available in injectable and buccal formulations to treat moderate to severe (acute) pain (e.g., Buprenex) and transdermal and buccal formulations to treat chronic pain (e.g., BuTrans® and Belbuca™). CAM2038 (buprenorphine FluidCrystal [FC] subcutaneous [SC] injection depot) once weekly (q1w) and once monthly (q4w), hereafter referred to as CAM2038 q1w and CAM2038 q4w, respectively, are ready-to-use, extended-release BPN products with a target of q1w or q4w SC dosing posology, respectively.

CAM2038 q1w and CAM2038 q4w were developed using the proprietary lipid-based and ambient responsive FC Injection depot technology. The principle behind the FC Injection depot is a liquid-to-gel phase transition, occurring immediately as the lipid-based FC system is exposed to *in vivo* conditions of SC tissue. The phase transition proceeds from the outside towards the center of the injected FC by absorption of minute quantities of water. Thus, injection of CAM2038 q1w or CAM2038 q4w into SC tissue results in an immediate and spontaneous formation of controlled BPN release matrix providing long-acting release *in vivo* with a minimum initial burst release. The dual nature of the FC system (i.e., a true liquid drug product *in vitro* before injection and stable gel *in vivo* after injection) enables a ready-to-use drug product in a prefilled syringe.

CAM2038 q1w and q4w are designed for convenient and safe SC injection using a prefilled syringe including a needle safety device and with no need for mixing or temperature adjustment from ambient temperature prior to administration. In addition, the injection volumes for CAM2038 q1w and q4w are relatively low (from 0.15 to 0.64 mL volume, depending on dose and product) and can be administered using a fine gauge needle (23 G). Overall, CAM2038 depots have been designed with a focus on enabling easy administration, dosing flexibility, and, importantly, minimizing risks of misuse, diversion, and poor patient compliance.

4.1.1. CAM2038 q1w (Once Weekly)

SC CAM2038 q1w has so far been investigated after single and repeated doses in 7 clinical trials in opioid-dependent subjects and healthy volunteers. An initial Phase 1/2 study assessed pharmacokinetics (PK), pharmacodynamics, and safety in opioid-dependent subjects (Study HS-07-307). The results showed that CAM2038 q1w was well tolerated, both locally and systemically. Importantly, no treatment-emergent serious adverse events (SAEs) were observed and drug-related local tolerability findings were limited to 4 of 42 subjects (9.5%). Three subjects experienced mild injection site pain and 1 patient exhibited transient injection site inflammation (mild) and injection site pruritus (moderate).

Two additional clinical Phase 1 studies were subsequently performed in healthy volunteers (under naltrexone blockade) to assess the PK and bioavailability of single and repeat doses of CAM2038 q1w versus repeated doses of sublingual (SL) BPN (i.e., at steady state) and single dose of intravenous (IV) BPN (Studies HS-11-426 and HS-13-487). These two studies demonstrated that after administration of the studied doses of CAM2038 q1w, the plasma concentrations corresponded to those obtained after administration of SL BPN at approved doses (i.e., 8 mg, 16 mg, or 24 mg doses). The BPN levels after administration of CAM2038 q1w were furthermore similar in healthy volunteers and subjects with opioid dependence. The systemic tolerability of CAM2038 q1w was good in both studies and similar to the reference products, IV and SL BPN. Local tolerability was very good with no adverse events (AEs)

reported in Study HS-11-426 (N_{safety}=60) related to injection site tolerability. Similarly, local tolerability of CAM2038 q1w was also very good in Study HS-13-487, featuring 4 repeat injections of CAM2038 q1w into the buttock site (1 subject reported 1 AE of injection site pain).

Based on these studies, the following main conclusions were drawn regarding the clinical properties of CAM2038 q1w:

- Extended BPN release over one week
- Dose proportionality and flexible/multiple dosing options
- Six- to 8-fold higher bioavailability versus SL BPN
- BPN plasma concentrations over 7 days within ranges of those produced by corresponding SL BPN doses at steady state (i.e., approved 8 mg, 16 mg or 24 mg doses)
- Less peak/trough fluctuation compared to SL BPN
- Repeated-dose administration suggest time-independent PK
- Good safety and systemic tolerability in subjects
- Safety in healthy volunteers comparable to IV and SL BPN treatments
- Good local tolerability in subjects and healthy volunteers

The clinical PK profile and good systemic and local tolerability of CAM2038 q1w evidenced in subjects in these 3 studies is also supported by a large body of data generated in non-clinical PK and toxicology studies in the dog, mini-pig, and rat of single and repeat SC doses of CAM2038 q1w, including repeat weekly doses of the FC vehicle formulation for 6 months. SC administration of CAM2038 q1w has been shown to be well tolerated both systemically and locally in the non-clinical studies. The treatment-related findings have been limited to clinical observations in agreement with, and considered related to, known pharmacological effects of the drug substance BPN, and to reversible, local inflammatory reactions at the SC site of injection. The latter findings were similar to the physiological response to a foreign body. The FC-related injection site findings appeared to be reversible and self-limiting, and only apparent at the immediate vicinity of test article deposition. In summary, non-clinical data have indicated no systemic toxicity associated with CAM2038 q1w or the FC injection depot vehicle.

4.1.2. CAM2038 q4w (Once Monthly)

SC CAM2038 q4w has been investigated in 5 studies, including one bridging clinical Phase 1 PK study in healthy volunteers versus repeat dose CAM2038 q1w (i.e., at steady state), repeat dose SL BPN (i.e., at steady state), and a single dose of IV BPN (Study HS-13-487). The following conclusions can be drawn regarding the clinical properties of CAM2038 q4w:

- Extended BPN release over 4 weeks
- Six- to 8-fold higher bioavailability versus SL BPN, comparable to CAM2038 q1w
- BPN plasma concentrations over 4 weeks comparable to CAM2038 q1w over one week, and to SL BPN over 24 hours at steady state (i.e., for approved 8 mg, 16 mg, or 24 mg doses)
- Predicted average concentration during a dosage interval at steady state (C_{ss,av}) and trough concentration during a dosage interval at steady state (C_{ss,trough}) values for CAM2038 q4w similar to CAM2038 q1w
- Safety profile comparable to IV and SL BPN treatments
- Good local tolerability

The most commonly reported drug-related AEs after CAM2038 q1w and CAM2038 q4w administration in Study HS-13-487 were nausea (63% of subjects), dizziness (54% of subjects), and vomiting (39% of subjects). The local tolerability was good, with 9 subjects experiencing 10 AEs that were assessed as related to CAM2038 q4w (injection site reactions, injection site pain, injection site induration, and application site bruise). Two SAEs were reported by 2 subjects after treatment with 192 mg CAM2038 q4w. The first SAE was an event of withdrawal reaction and the second SAE was an event of dehydration due to nausea and vomiting. Both SAEs were assessed as related to CAM2038 q4w (withdrawal reaction was also assessed as related to the concomitant treatment with naltrexone) and the event of withdrawal reaction qualified for reporting as a suspected unexpected serious adverse reaction. There were no deaths or any other significant AEs, and most of the AEs were mild and transient. Analysis of clinical chemistry, hematology, and urinalysis parameters did not suggest any significant safety issues for CAM2038 q4w.

The non-clinical assessment of CAM2038 q4w and the FC vehicle, supported by publicly available data for the drug substance BPN, and for the components of the vehicle, suggests safe use of CAM2038 q4w for the proposed clinical development. This conclusion is further supported by results from non-clinical and clinical studies of CAM2038 q1w, comprising the same active substance and functional lipid components.

Additional information about CAM2038 can be found in the current version of the Investigator's Brochure.

4.1.3. Completed CAM2038 Phase 2 and Phase 3 Studies

There are four completed Phase 2 and Phase 3 clinical studies of CAM2038, HS-11-421, HS-13-478, HS-15-549 and HS-14-499. Please refer to the Investigator's Brochure for more detailed investigative study and safety information.

HS-11-421 (completed)

This was a randomized, double-blind, double-dummy, active-controlled, parallel group, multicenter study, designed to evaluate the non-inferiority of CAM2038 compared to an existing standard of care (SL BPN/naloxone [NX]) in initiation and maintenance treatment with BPN in subjects with opioid use disorder. The study involved 4 phases: Screening, Phase 1 (weekly visits, for 12 weeks), Phase 2 (monthly visits, for 3 months), and Follow-up.

A total of 428 subjects were randomized in the study, whereof 213 subjects were treated with CAM2038 and 215 subjects with SL BPN/NX. The study has been completed with no significant unusual or unexpected safety signals or concerns reported.

HS-15-549 (completed)

This was a Phase 2, open-label, partially randomized, 3-treatment group study designed to evaluate the steady state PK of BPN and norbuprenorphine (norBPN) following multiple weekly SC administrations of CAM2038 q1w at different injection sites (Group 1), following multiple monthly SC administrations of CAM2038 q4w (Group 2) in opioid-dependent subjects with a history of chronic non-cancer pain and following multiple monthly SC administrations of CAM2038 q4w (Group 3) in opioid-dependent subjects with a history of chronic non-cancer pain who were currently taking 24 mg of SL BPN daily. The trial involved up to 4 phases: Screening, Treatment, Follow-up and Open Label Safety Extension. Approximately 55 subjects were to be enrolled. The study has been completed and there were no unusual safety signals or concerns identified.

HS-13-478 (completed)

This was a Phase 2 multi-site, randomized, double-blind, repeat-dose Phase 2 study to evaluate the degree and duration of action of multiple doses of CAM2038 q1w in blocking the effects of a mu opioid receptor agonist (hydromorphone) in subjects with moderate or severe opioid use disorder. The study involved 4 phases: Screening, Qualification, Treatment, and Follow-up. In the treatment Phase, subjects received one of the following treatments (based on a randomization in a 1:1 ratio, stratified by gender and blinded): Group A received CAM2038 q1w 24 mg SC injection (22 subjects) and Group B received CAM2038 q1w 32 mg SC injection (25 subjects).

Each of the Hydromorphone Challenge Sessions in the Qualification Phase and Treatment Phase consisted of the injection of 3 doses of IM hydromorphone (0 mg [placebo], 6 mg and 18 mg) administered once daily over 3 consecutive days in randomized blinded order. Subjects were randomized in a 1:1:1:1:1:1 ratio to 1 of 6 treatment sequences according to two 3×3 William squares.

HS-14-499 (completed)

This was a Phase 3, open-label, multicenter, 12-month (48-week) safety study in subjects with opioid use disorder, consistent with standard practice for long-term safety studies. This safety study utilized CAM2038 q1w and CAM2038 q4w and had 3 phases: Screening, Treatment, and Follow-up. The trial is completed and ended when at least 100 subjects have been exposed to CAM2038 for 48 weeks. There were no unusual safety signals or concerns identified in the study.

4.2. Study Rationale

Chronic low back pain (CLBP) is a significant cause of pain and disability costs worldwide ([Volinn et al, 2009](#); [Vos et al, 2012](#)). While most subjects with CLBP show significant improvements within 3 months, a proportion of subjects experience persistent pain (≥ 3 months) and may have limited quality of life and physical function ([Shekelle et al, 1995](#); [Thomas et al, 1999](#)). Management of CLBP may be achieved through several modalities, including opioid pharmacotherapy. Despite their proven efficacy, the use of opioids is often limited due to concerns regarding safety and tolerability and concerns pertaining to drug abuse and diversion that may arise with long-term therapy for treatment of persistent pain. However, for many subjects with CLBP, opioid therapy may be the only effective treatment. BPN is an effective analgesic with a potency 25 to 50 times that of morphine ([Jasinski et al, 1978](#); [Cowan et al, 1977](#)). Dose-dependent analgesia has been observed with intramuscular (IM) doses up to 10 mg. Respiratory depression is minimized due to the well-characterized ceiling effect at higher doses ([Hans and Robert, 2009](#)). Clinically, there is also a less marked effect of BPN on gastrointestinal transit times, with a lower incidence of constipation relative to full mu-opioid receptor agonists ([Mercadente, 2009](#)). In addition, the slow dissociation of BPN from receptors results in a long duration of effect and minimizes withdrawal symptoms upon discontinuation ([Sittl et al, 2005](#)). Transdermal BPN has proven effective in subjects with chronic cancer and non-cancer pain, with a reduction in the need for additional oral analgesics and improved quality of life ([Mercadente, 2009](#); [Dahan et al, 2005](#); and [Griessinger et al, 2005](#)).

A number of treatment goals have been proposed for improved patient therapy, many of which are based on World Health Organization (WHO) recommendations, including providing a stable plasma drug concentration to ensure long lasting and effective pain relief, formulations that provide a long duration of action, and an improved quality of life. By using the transdermal formulation of BPN, the rate of drug delivery can be controlled and stable plasma concentrations achieved. However, transdermal BPN may still be subject to abuse and diversion, as the patches may be swallowed or the BPN may be extracted from the patches and injected or ingested, including improperly disposed patches ([Tompkins et al, 2014](#); [Belbuca™ Prescribing Information, October 2015](#)). Transdermal systems may also be accidentally ingested, particularly by children. Traditional opioid therapies intended for the treatment of chronic pain (e.g., modified or extended-release formulations of full μ -opioid receptor agonists such as morphine,

oxycodone, hydrocodone, and hydromorphone) are even more subject to diversion and abuse, resulting in significant public health concerns (Sittl et al, 2005 and Likar et al, 2003).

The sustained and stable BPN plasma concentration associated with administration of CAM2038 q1w and q4w may provide an ideal treatment modality for many CLBP subjects. The PK profile of CAM2038 q1w indicates that a rapid and long-acting release of BPN should lead to rapid and smooth onset of action, in combination with a prolonged and stable treatment effect for at least 7 days following a single dose of CAM2038 q1w or up to 4 weeks following a single dose of CAM2038 q4w. Thus, the PK profiles of CAM2038 q1w may help to improve tolerability during initiation of treatment. Like transdermal formulations, CAM2038 may also be suitable for those subjects with difficulty swallowing.

The profiles of CAM2038 provide an alternative to existing oral opioid medications, with the potential added benefit of obtaining consistent and stable plasma levels of BPN. This profile removes the need to take daily medications and helps to prevent diversion and accidental pediatric exposures, which continue to be important public health goals of the Food and Drug Administration (FDA) and Center for Disease Control and Prevention (Frieden and Houry, 2016). Furthermore, the route of administration (i.e., depot injection) of CAM2038 may reduce the risks of diversion and abuse, even when compared to transdermal opioid formulations.

While the efficacy of transdermal and transmucosal BPN in managing pain and improving function has previously been demonstrated in subjects with CLBP (Salinas et al, 2012; Rauck et al, 2016), the anesthetic efficacy of BPN administered as CAM2038 q1w or CAM2038 q4w SC injections has not yet been evaluated. The present study will be conducted to evaluate the efficacy and safety of CAM2038 compared to placebo in subjects with moderate to severe CLBP over a period of 12 weeks during the Double-Blind Phase. In addition, the safety of CAM2038 will be evaluated from the Open-Label Titration Phase and throughout the Open Label Safety Extension Phase.

4.3. Dose Rationale

The 4-mg weekly starting dose of CAM2038 q1w correspond to a daily morphine equivalent dose (MED) of 28.5 mg, using a more conservative conversion factor of 50 from BPN to morphine; thus, representing safe and suitable starting doses for subjects receiving ≥ 30 mg of morphine daily. In this study, subjects will be titrated to effect. An indicative a priori transition from daily morphine dose to weekly CAM2038 doses and monthly CAM2038 dose is given in Table 1 and Table 2 below, respectively:

Table 1: Conversion from Daily Morphine to Once Weekly CAM2038 Doses

Daily Morphine Dose (mg)	Daily Titration Morphine Dose, 75 % (mg)	Starting Once Weekly Dose
40 to <80	30 to 60	4 mg CAM2038
80 to 120	60 to 90	8 mg CAM2038
>120 to 160	90 to 120	16 mg CAM2038
>160 to 320	120 to 240	24 mg CAM2038
>320	>240	32 mg CAM2038

Table 2: Conversion from Once Weekly CAM2038 to Once Monthly CAM2038 Dose

Once Weekly Dose	Corresponding Once Monthly CAM2038 Dose
4 mg CAM2038	No corresponding monthly dose. Subjects will be kept on CAM2038 once weekly.
8 mg CAM2038	No corresponding monthly dose. Subjects will be kept on CAM2038 once weekly.
12 mg CAM2038	No corresponding monthly dose. Subjects will be kept on CAM2038 once weekly.
16 mg CAM2038	64 mg CAM2038
24 mg CAM2038	96 mg CAM2038
32 mg CAM2038	128 mg CAM2038

The MED will be calculated using the conversion factor for each opioid as described in [Table 3](#) (McPherson, 2009). Subjects taking methadone are allowed to screen; however, the down titration process should be discussed with the Medical Monitor.

Table 3: Opioid Conversion to Morphine Equivalent Dose

Equianalgesic Opioid Dosing			
Drug	Equianalgesic Doses (mg)		
	Parenteral	Oral	Sublingual
Sublingual Buprenorphine	NA	NA	1.5
Belbuca™ buccal film	NA	0.3	NA
Morphine	10	30	NA
Codeine	100	200	NA
Hydrocodone	NA	30	NA
Hydromorphone	1.5	7.5	NA
Meperidine	100	300	NA
Oxycodone	10*	20	NA
Oxymorphone	1	10	NA
Tramadol	100*	120	NA
		Morphine (PO) Equivalents	
*Fentanyl Patch 25mcg/hr (One patch q3 days)	NA	60 mg / d	NA
Butrans patch 10mcg/hr (One patch q week)	NA	80 mg / d	NA
*Methadone 20 mg PO qd	NA	40 mg / d	NA

* Contact Medical Monitor to discuss

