Subjects who were previously on BPN prior to Screening will not need to participate in the morphine IR phase. However, subjects who were previously on BPN will be required to refrain from taking BPN for 12-24 hours as a washout prior to starting open label titration on CAM2038.

Following the morphine IR treatment, subjects will enter the Titration Phase. On Day 1 of the Titration Phase, subjects will return to the clinic after a washout of at least 12 hours from their last morphine IR dose, or 12-24 hours from their last BPN dose. Subjects who report a CLBP of ≥ 5 on the API scale and have a Clinical Opiate Withdrawal Scale (COWS) score of ≥ 5 , will receive a BPN test dose (Buprenex[®] 0.30 mg intramuscular [IM] injection) at the clinical site. After the Buprenex test dose, subjects will be assessed for any changes in QTcF (Fridericia’s corrected QTc) and withdrawal. Subjects who tolerate the BPN test dose, do not show an increase >30 ms in

QTcF within 1 hour after the test dose, and have a COWS score of <5 within 15 minutes after the test dose will receive the first dose of SC CAM2038 q1w within 4 hours (+30 minutes) after the test dose (4 mg CAM2038 for subjects whose screening MED was between 40 mg/day and 79 mg/day; and 8 mg CAM2038 for subjects whose screening MED was ≥ 80 mg/day).

During the first week of the Titration Phase, subjects who experience significant pain may, at the discretion of the investigator, receive an additional dose at their corresponding CAM2038 q1w dosing level (4 mg or 8 mg respectively) on Day 3, 4 or 5. Subjects will then attend clinic visits every week for dosage adjustment. Dose adjustments will be made by increasing the dose level of CAM2038 q1w at the scheduled weekly visits (doses of 4 mg, 8 mg, 12 mg, 16 mg, 24 mg, or 32 mg per week). Subjects who require doses >32 mg/week will be discontinued from the study.

Rescue medication, consisting of hydrocodone/acetaminophen 5 mg/325 mg every 4 to 6 hours (q4-6h), may be taken during the Titration Phase as needed (prn), up to 15 mg/975 mg/day (3 tablets) for subjects whose MED at screening was 40-79 mg/day or up to 30 mg/1950 mg/day (6 tablets) for subjects whose MED at screening was ≥ 80 mg/day). The goal of the Titration Phase is to reach a stable dose of CAM2038 q1w that produces analgesia, by the end of the 10-week period.

Eligible subjects will receive CAM2038 titrated to a dose that meets the following criteria:

- Provides analgesia (i.e., 7-day mean API ≤ 4)

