6.1.2. Open Label Titration Phase

Following the morphine IR treatment, subjects will enter the Titration Phase. On Day 1 of the Titration Phase, subjects will return to the clinic after a washout of at least a 12-hour from their last morphine IR dose, or 12-24 hours from their last BPN dose. Subjects who report a CLBP of ≥ 5 on the API scale and have a Clinical Opiate Withdrawal Scale (COWS) score of ≥ 5 , will receive a BPN test dose (Buprenex 0.30 mg IM injection) at the clinical site. After the Buprenex test dose, subjects will be assessed for any changes in QTcF (Fridericia's corrected QTc) and withdrawal. Subjects who tolerate the BPN test dose, do not show an increase >30 ms in QTcF within 1 hour after the test dose, and have a COWS score of <5 within 15 minutes after the test dose will receive the first dose of SC CAM2038 q1w within 4 hours (+30 minutes) after the test dose (4 mg CAM2038 for subjects whose screening MED was between 40 mg/day and 79 mg/day; and 8 mg CAM2038 for subjects whose screening MED was ≥ 80 mg/day).

During the first week of the Titration Phase, subjects who experience significant pain may, at the discretion of the investigator, receive an additional 4 mg (for subjects whose screening MED was 40-79 mg/day) or 8 mg CAM2038 (for subjects whose screening MED was ≥ 80 mg/day), on Day 3, 4 or 5. Dose adjustments will be made by increasing or decreasing the dose level of CAM2038 q1w at the scheduled weekly visits (doses of 4 mg, 8 mg, 12 mg, 16 mg, 24 mg, or 32 mg per week). Subjects who require doses >32 mg/week will be discontinued from the study.

Rescue medication, consisting of hydrocodone/acetaminophen 5 mg/325 mg every 4 to 6 hours (q4-6h), may be taken as needed (prn) up to 15 mg/975 mg/day (three tablets) for subjects whose screening opioid dose was between 40 and 79 mg/day MED or 30 mg/1950 mg/day (six tablets) for subjects whose screening opioid dose was ≥ 80 mg/day MED. The goal of the Titration Phase is to achieve a stable dose of CAM2038 q1w that produces analgesia, by the end of the 10-week period.

Eligible subjects will receive CAM2038 titrated to a dose that meets the following criteria (see also Section 7.4):

- Provides analgesia (i.e., 7-day mean API ≤ 4)
- The API is at least 2 points below the value at the start of CAM2038 titration
- The dose of CAM2038 is well-tolerated for 7 days before randomization (no adverse effects that require a change in study dosing or interruption)

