6.1.3. Double-Blind Phase

Subjects who are stabilized and responding to their CAM2038 q1w dose (4, 8, 12, 16, 24, or 32 mg/week) at the end of the Titration Phase and who fulfill the pre-defined randomization criteria will be randomized to one of two treatment groups in the 12-week Double-Blind Phase:

- Group 1: CAM2038 q1w or CAM2038 q4w SC injections
- Group 2: placebo q1w or placebo q4w SC injections

During the Double-Blind Phase, all subjects who are receiving 4, 8 or 12 mg CAM2038 q1w at the end of the Titration Phase will be randomized to continue their respective CAM2038 q1w dosing of 4 mg, 8 mg or 12 mg CAM2038, or to matching placebo q1w for a total treatment duration of 12 weeks. Subjects who are receiving 16 mg, 24 mg or 32 mg CAM2038 q1w at the end of the Titration Phase will be randomized to CAM2038 q4w (64 mg, 96 mg or 128 mg, respectively) or to matching placebo q4w for a total treatment duration of 12 weeks.

Figure 1: Overview of Study Design

¹ One booster is allowed on Day 3-5 after the first CAM2038, 4 or 8 mg injection. If booster is taken, the next dose on week 2 will be 8 or 12 mg, otherwise stay at 8 mg. Then titration is weekly up to 10 weeks. Final Study Visit is 1 week after the last CAM2038 q1w dose for q1w subjects and 4 weeks after the last q4w dose for q4w subjects. Follow-up is within 4 weeks after the Final study visit.

IR = immediate release; MED=morphine equivalent dose; q1w=once weekly; q4w=once monthly; R= randomization. There will be a Final Study Visit or Early Termination and one Follow-up Call.

Rescue medication, hydrocodone/acetaminophen 5 mg/325 mg q4-6h prn, will be allowed during the Double-Blind Phase (up to three tablets or 15 mg/975 mg/day for subjects whose MED at screening was between 40-79 mg/day and up to six tablets or 30 mg/1950 mg/day for subjects whose MED at screening was ≥80 mg/day). Whenever subjects take rescue medication, they must record their pain intensity “at that moment” prior to taking rescue medication in the electronic diary.

6.1.4. Follow-up Phase for Subjects Not Transitioning to the Open Label Safety Extension Phase

A Final Study Visit will take place 1 week after the last CAM2038/placebo q1w dose or 4 weeks after the last CAM2038/placebo q4w dose. At the Final Study Visit (or early termination), subjects will be transitioned back to standard care or to their treatment prior to study entry. Subjects will then be contacted

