8.1.3. Titration Phase

After administration of the Buprenex test dose on Day 1, subjects who tolerate the test dose, do not show an increase of > 30 ms in QTcF within 1 hour, and have a COWS score of < 5 within 15 minutes after the test dose will receive their first dose of CAM2038 q1w within 4 hours (+ 30 minutes) after the test dose. Subjects whose screening opioid dose was between 40 mg and 79 mg/day MED will be started on 4 mg CAM2038 q1w. Subjects whose screening opioid dose was ≥ 80 mg/day MED will be started on 8 mg CAM2038 q1w. During the first week of the Titration Phase, subjects who experience significant pain may, at the discretion of the investigator receive a second dose of CAM2038 at their respective dose (4 mg for subjects whose screening MED was 40-79 mg/day; 4 or 8 mg CAM2038 q1w for subjects whose screening Med was ≥ 80 mg/day) on Day 3, 4, or 5. Subjects will then attend clinic visits every week for dosage adjustment. Dose adjustments will be made by increasing or decreasing the dose level of CAM2038 q1w at the scheduled weekly visits (doses of 4 mg, 8 mg, 12 mg, 16 mg, 24 mg, or 32 mg per week).

The maximum dose within a 7-day period cannot exceed 32 mg. Subjects who require doses higher than 32 mg/week will be discontinued from the study. The dosing of CAM2038 q1w will be titrated with the purpose of achieving a stable dose of CAM2038 q1w by the end of the 10-week Titration Phase.

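### The early-titration dosing text contradicts itself on starting dose, first-week booster, week-2 dose and direction of adjustment, and should be reconciled into one table

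*Protocol*

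**What the plan says.** **First dose.** Section 4.3 leads into Table 1 with "An indicative a priori transition from daily morphine dose to weekly CAM2038 doses", just after saying "In this study, subjects will be titrated to effect". The last column of the table is headed "Starting Once Weekly Dose". It gives 4 mg for 40 to below 80 mg morphine/day, 8 mg for 80 to 120, 16 mg for above 120 to 160, 24 mg for above 160 to 320, and 32 mg above 320. Section 8.1.3 says that subjects with a screening MED of 80 mg/day or more "will be started on 8 mg CAM2038 q1w", with no higher band. The synopsis, Section 6.1.2, Figures 2 and 3, footnote 15 of Table 5 and footnote o of Table 9 agree with Section 8.1.3.

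**Booster on Day 3, 4 or 5.** Section 8.1.3 first ties the second dose to the subject's own level and then, in the same sentence, writes "4 or 8 mg CAM2038 q1w for subjects whose screening Med was" 80 mg/day or more. The synopsis (in two places) and Section 6.1.2 give those subjects 8 mg.

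**Week 2.** The note to Figure 1 (Section 6.1.3) covers a first injection of 4 or 8 mg and adds: "If booster is taken, the next dose on week 2 will be 8 or 12 mg, otherwise stay at 8 mg". The notes to Figures 2 and 3 describe the booster but have no week-2 rule.

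**Direction.** The synopsis has "Dose adjustments will be made by increasing the dose level of CAM2038 q1w at the scheduled weekly visits". Section 6.1.2 has "Dose adjustments will be made by increasing or decreasing the dose level of CAM2038 q1w at the scheduled weekly visits", and Section 8.1.3 and the Table 5 and Table 9 footnotes say the same.

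**The concern.** These passages govern the first two weeks on a long-acting opioid depot, starting on the day the subject leaves the previous opioid. Inclusion criterion 5 (Section 7.1) sets a floor of 40 mg/day MED and no ceiling, so subjects in the upper three rows of Table 1 can be enrolled. About 85 sites are planned. Staff who consult different pages would find different answers on the size of the booster, the week-2 dose and whether a step down is foreseen. If they took the Table 1 heading at its word, they would also find a different first dose.

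The titrated dose matters later as well. It decides whether a subject goes into the weekly or the monthly regimen, which is the randomisation stratum, and at what dose (Sections 8.1.4 and 8.3). Titration should therefore be run the same way everywhere.

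**Working it through.** **1. Reproduce the protocol's own figures.** Section 4.3 converts a weekly dose to daily MED with a factor of 50: weekly dose ÷ 7 × 50. For 4 mg, 4 ÷ 7 × 50 = 28.57; the protocol prints 28.5. The middle column of Table 1 is 75% of daily morphine: 0.75 × 40, 80, 120, 160, 320 = 30, 60, 90, 120, 240, as printed.

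**2. First dose, table against operative text.**

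| Daily morphine (mg) | Table 1 | Operative sections | Ratio | Table 1 dose as MED/day (dose ÷ 7 × 50) |
|---|---|---|---|---|
| 40 to <80 | 4 mg | 4 mg | 1 | 28.57 |
| 80 to 120 | 8 mg | 8 mg | 1 | 57.14 |
| >120 to 160 | 16 mg | 8 mg | 16/8 = 2 | 114.29 |
| >160 to 320 | 24 mg | 8 mg | 24/8 = 3 | 171.43 |
| >320 | 32 mg | 8 mg | 32/8 = 4 | 228.57 |

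The two sources agree up to 120 mg/day and part company above it.

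**3. Could the table be read by the morphine taken just before Day 1?** Subjects not on buprenorphine receive immediate-release morphine at 15 × 3 = 45 or 15 × 4 = 60 mg/day (Section 6.1.1). In the middle column, 45 lies in the 4 mg row and 60 on the printed boundary of the 4 and 8 mg rows. On that reading nobody taking immediate-release morphine reaches the 16, 24 or 32 mg rows. In the first column, 60 mg/day falls in the 4 mg row, while the text gives those subjects 8 mg. The protocol does not say which morphine dose is meant, so the table needs a clarifying statement on any reading.

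**4. Booster at MED 80 or more.** Section 8.1.3 permits 4 or 8 mg; the synopsis and Section 6.1.2 permit 8 mg. An 8 mg booster is consistent with every passage. A 4 mg booster is consistent only with the second half of the Section 8.1.3 sentence.

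**5. Week 2.** Week-1 totals with a booster are 4 + 4 = 8, 8 + 4 = 12 or 8 + 8 = 16 mg. The note's 8 or 12 mg matches the first two totals and has no counterpart for the third. Without a booster, the note has subjects remain at 8 mg, which can describe only those who started on 8 mg. The 4 mg starter without a booster is not covered. Sections 6.1.2 and 8.1.3 and Table 5 fix no week-2 dose and allow adjustment at each weekly visit over 4 to 32 mg.

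**6. Direction.** The synopsis names increases; Sections 6.1.2 and 8.1.3 and Tables 5 and 9 name increases and decreases.

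**The case against.** The strongest reply is that Table 1 is background. It sits in the dose rationale, is titled as a conversion and is introduced as indicative, and all the operative passages agree on 4 or 8 mg. The 7-day limit of 32 mg in Section 8.1.3 points the same way: a 32 mg first dose would leave no room for a booster, since 32 + 4 = 36 and 32 + 8 = 40. This stands. A reader might infer that sites will give first doses up to four-fold apart, but that would require a site to dose from a rationale table against every operative section. What remains is a column heading that calls the values starting doses, with nothing in Section 4.3 to say that they do not apply on Day 1.

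The reply does not reach the booster, the Figure 1 note or the direction of adjustment, which are conflicts within the operative text. Stronger readings are tempting there too, and the documents do not support them:

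- That the Figure 1 note doubles the dose of a 4 mg starter who had no booster. Remaining at 8 mg presupposes being on 8 mg, so the note leaves that subject out and does not order an increase.
- That a week-2 dose of 8 or 12 mg contradicts a 16 mg week-1 total. A lower next dose is not in itself a contradiction, and its suitability is a clinical matter.
- That the synopsis forbids stepping down, so that subjects who do not tolerate a level are lost before randomisation. The synopsis is silent on decreases; it does not exclude them, and the body of the protocol provides for them.
- That the randomised comparison is biased. All of this dosing precedes randomisation, which is 1:1 within the weekly and monthly regimens, after at least 2 weeks on a stable dose.

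**Conclusion.** Wrong as written, as an internal inconsistency that should be fixed. Four places disagree: the Table 1 heading against the operative first dose, the booster at MED 80 or more, the Figure 1 week-2 rule, and the direction of adjustment. The largest numerical gap is 2-, 3- or 4-fold in the first dose above 120, 160 and 320 mg/day. It applies only if a site doses from Table 1 by pre-study morphine; because the operative sections agree, it is a worst case and not an expected outcome. The booster gap is 4 against 8 mg. The other two are a gap in coverage with a conflicting rule, and an incomplete statement.

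The consequence is for patient safety and uniform conduct of titration. No effect on the treatment estimate, the error rate or the number of subjects reaching randomisation has been shown. The week-2 part rests on the printed note to Figure 1, read without its drawing. Nothing here says which dose or rule is right.

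**What to change.** Reconcile the synopsis (methodology and investigational product text), Table 1, Section 6.1.2, the Figure 1 note, Section 8.1.3 and the Table 5 and Table 9 footnotes into one dosing table. It should have a row for each combination of screening MED band and booster status, and columns for Day 1, the Day 3-5 booster, week 2 and later weekly adjustments, including whether decreases are allowed. The other sections should refer to that table and not restate it. If Table 1 is only an equivalence guide, retitle its last column so that it cannot be taken for a Day 1 dose, and state which morphine dose it is entered with. The sponsor makes the clinical choice in each cell.

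The cost is protocol wording (one new table, one column heading, the repeated dosing text and footnotes) and a memo to sites, handled under the amendment procedure in Section 12.6. Sample size, visits and analysis do not change.
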